6.3 Observation period

6.3.1 Inclusion period

The urologist / nephrologist will recruit patients as they come to the consultation and meet the inclusion and exclusion criteria, according to the consecutive sampling technique. The assignment of the study treatment will be carried out randomly, according to the previously established code that will be assigned to each patient as they are included in the study.

The expected duration for the recruitment of patients will be 3 months with a follow-up period until the stent is extracted, which is expected to be a maximum of 2 months. The recruitment of the participating centers will be competitive.

6.3.2 Follow-up period

The follow-up will be 3 weeks up to a maximum of approximately 2 months, depending on the time from the inclusion visit (V0) to the extraction of the stent (Vf). During this period, the patient will self-monitor their urinary pH level at home and register the respective data with the domiciliary CRD. The patient will be offered the possibility of registering the home self-management data directly to an online CRD through a personalized link that the researcher will provide during the inclusion visit and that will be generated through a computer program. If you only register it on paper, you must deliver it to the researcher at the next visit.

6.3.3 Baseline Visit - V0 (inclusion)

The researcher will consecutively include the patients as they come to their consultation. The investigator will inform the patient about the study and will provide the information sheet. In case the patient agrees to participate in the study, they must sign the informed Consent Form that the researcher will also provide. Subsequently, the researcher will ensure that the patient meets all the inclusion / exclusion criteria and proceed to confirm their inclusion in the study. If the patient is eligible but does not give informed consent and / or does not meet any of the inclusion / exclusion criteria, then the investigator will add a new case to the list of eligible patients without recording any other information related to the patient.

Sociodemographic data and medical and family history of interest will be recorded, as well as the date and reason for stent placement. The data will be recorded necessary to classify patients according to the "Blockage risk factor" 23. In addition, a urine test of 2 hours fasting will be requested.

At the end of the visit, the patient will be given the treatment assigned by randomization and the link to the electronic domicile CRD and on paper. The patient will be reminded that at the next visit they should return (empty or not) the blisters of the treatment administered.

NOTE: For reasons derived from the logistics and the tests to be performed with the stent, researchers should try to enter the data in the online CRD in real time (or within a 24 hour timeframe) both at the time of placement of the stent as of extraction. This will allow a follow-

up and an appropriate time of logistical management that guarantees that the stents arrive in optimal conditions for their study to the specialized center of Palma de Mallorca.

6.3.4 Visit Final Control - Vf (stent removal)

The time of the final visit will not be determined by protocol but according to the moment in which, by usual clinical practice, the double j stent is extracted in a programmed manner (which should be between 3 and 8 weeks after the baseline visit). During this visit, the data regarding the symptoms perceived by the patient during the time with the stent will be recorded, data relative to the received treatment (adherence, presence of adverse effects, date of beginning and end of the pH control, complications derived from the stent and data on stent removal (date, complications, presence / degree of calcification, etc.) and this will be sent (after conditioning) * to be analyzed by an expert to determine the presence of any of the different stages of calcification (presence of bacterial biofilm, incrustations and / or calcifications.) During this visit, the patient will deliver his / her home diary with the pH control data and annotated supplement record (as long as it has not already been registered directly with the home eCRD) and will also transfer the product excess (food supplement blisters) and, if possible, also empty blisters.

On the other hand, pharmacoeconomic data will also be recorded in order to determine the cost-effective profile of the intervention.

* The conditioning of the stent for storage and subsequent delivery to the specialist who is going to carry out his study is described in the Investigator's Manual.

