6.2.2 Exclusion criteria

- Patients with basic pathologies that, according to the researcher's criteria, are not susceptible to the recommendation of the food supplement object of study.
- Patients who have scheduled the extraction of the double J stent before 3 weeks from the baseline / inclusion visit.
- Uric and cystinuric patients that require pH control different from that established in the study protocol.

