6.4 Description of the intervention

The patients of the experimental group will receive the food supplement Lit-control®pH Down to help maintain the urinary pH at the levels considered as preventive for stent calcification (pH <6.2), with the indicated guideline of 3 capsules per day. On the contrary, the control group will receive a placebo product with similar organoleptic characteristics with the same dosage. Both groups will use the Lit-Control® pH Meter device for urinary pH self-monitoring as well as receiving the same indications for stent care.

The intervention group will be assigned to each patient according to the assigned code in order of inclusion to the study and that will serve for the randomization of the patients.

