7 VARIABLES AND MEASURING INSTRUMENTS

7.1 Main valuation variables

- Score on the scale of incrustation (main variable of effectiveness):
 - or 0 (Without inlay).
 - or 1 (Sporadic calcifications less than 1-2 mm²).
 - or 2 (Calcifications of wide areas greater than 1-2 mm²).
 - or 3 (Complete block).
- Urinary pH level and control of it below 6.2 (urine 2h fasting and home self-control with Lit-control®pH Meter).
- Reason for stent placement (approximately 90% is expected to be urolithiasis).
- Obstruction risk factor²³.
- Stent analysis / observation (presence of biofilm, degree of incrustation).
- Double J stent study:
 - o Scanning electron microscopy + micro-analysis by dispersive energy of RX: type and size of the crystals formed.
 - or ICP-AES spectroscopy (degree of global calcification of each end: Ca, Mg and P).
- Presence (Yes / No) and Degree of calcification (I-V) (Annex 7) ²⁴.

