7.2 Secondary valuation variables

- Sociodemographic and anthropometric variables (sex, age, weight, height, BMI, marital status, work situation, toxic habits).
- Family history of obstructive uropathies.
- Personal clinical history of interest (previous nephritic colic, kidney transplant, acute pathology of interest, chronic pathology (HBP, Chronic Kidney Disease, Diabetes and others).

- Anatomical alterations in the urinary system.
- Previous incidence of obstructive uropathy (urolithiasis, stenosis and ureteral injuries, retroperitoneal fibrosis).
- Previous need for stent (indwelling stent reason, date of stent placement and removal, type of stent and symptoms (if any) associated with it)
- Date of placement and removal of the double J stent (current) and Total time with double J stent until its withdrawal (days).
- Total pH control time (days).
- Urine analysis of 2 hours in basal fasting (volume of urine, pH, creatinine, uric acid).
- Urine culture (infection: yes / no).
- Complications observed due to placement or permanence of the stent and symptoms associated with indwelling stent.
- Image of the stent (scanner or X-ray).
- Adherence to treatment / recommendations of the doctor.
- Adverse events attributable to the treatment or study recommendations.
- Data on stent removal (date, complications, type of procedure and duration of extraction).
- Satisfaction of the researcher with preventive therapy.
- Patient satisfaction with preventive therapy.
- Pharmacoconomic data (direct costs): stent placement intervention, consultation visits, emergency visits, hospitalizations, medication administered, intervention (cost and type) for stent removal and total direct cost of the patient during the study (estimated at from the data provided by the center).

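### The primary incrustation score is read at a removal date left open from 3 to 8 weeks; the stated comparison ignores time, and the planned date is not recorded before allocation

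*Protocol*

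**What the plan says.** - **Endpoint (7.1).** The main efficacy variable is a single four-grade score: "Score on the scale of incrustation (main variable of effectiveness". It is read on the extracted stent.
- **Reading time (6.3.4).** "The time of the final visit will not be determined by protocol but according to the moment in which, by usual clinical practice" the stent comes out, and it is to be "extracted in a programmed manner (which should be between 3 and 8 weeks after the baseline visit". Section 6.3.2 agrees, tying each patient's follow-up to removal: "The follow-up will be 3 weeks up to a maximum of approximately 2 months, depending on the time from the inclusion visit (V0) to the". Section 7.4, by contrast, labels the final visit as 8 weeks in its adherence end point.
- **Start of the clock (6.2.1).** At V0 the stent may be up to a week old or not yet placed, so time from V0 is not the same as dwell.
- **Planned date (6.2.2, 6.3.3).** An exclusion criterion looks at it: "Patients who have scheduled the extraction of the double J stent before 3 weeks from the baseline / inclusion visit". The V0 data listed in 6.3.3 include the date of and reason for placement, but not the planned removal date.
- **Actual dwell (7.2).** It is collected as a secondary variable: "Total time with double J stent until its withdrawal (days".
- **Early removal (6.2.3).** Removal within 3 weeks of baseline is a discontinuation criterion.
- **Comparison (8.2).** Student's t-test, or Mann-Whitney if normality fails, with no term for time. Section 6.8 sizes the trial on Mann-Whitney.
- **Who sees pH (6.4, 6.3.4).** "Both groups will use the Lit-Control® pH Meter device for urinary pH self-monitoring". On paper records: "During this visit, the patient will deliver his / her home diary with the pH control data".

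**The concern.** Section 2 of the protocol describes incrustation as a process that progresses, faster in some patients than in others. A score taken anywhere between 21 and 56 days therefore mixes the effect of the supplement with length of exposure.

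Two consequences need to be kept apart.

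1. **Precision.** Even if dwell has the same distribution in both arms, its spread is variation that the stated test leaves unexplained.
2. **Bias.** If actual dwell ends up differing by arm, the score differs for a reason other than the supplement's effect on incrustation. Possible routes are symptoms, stent complications, the 3-week discontinuation rule, or patients reacting to their own daily pH readings, which the capsule blinding does not hide. A gap in either direction matters. Earlier removal on placebo hides a benefit; earlier removal on the supplement imitates one.

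Actual stent days would show that a gap exists. Without the planned date they cannot show whether it was a chance imbalance in the plans or a departure from plan after allocation.

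**Working it through.** **1. The plan's own sample size.** Inputs from 6.8: effect size 0.6, power 80%, Mann-Whitney, 10% loss. Alpha is not stated; two-sided 0.05 is assumed. The normal formula gives 2 × ((1.960 + 0.842)/0.6)² = 43.6 per arm. Dividing by the Mann-Whitney efficiency 3/π gives 45.7. The same calculation with the noncentral t gives 47 per arm, or 94. Then 94/0.9 = 104.4, rounded up to 105. Both stated figures reproduce, and neither allows for variation in dwell.

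**2. The window.** 3 to 8 weeks is 21 to 56 days, and 56/21 = 2.7-fold.

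**3. What an arm gap would do, by arithmetic.** The protocol gives neither the distribution of dwell nor its relation to the score. Assumed: dwell uniform over 3-8 weeks, SD = 5/√12 = 1.44 weeks; correlation r of 0.3 to 0.5 with latent incrustation (r² = 9% to 25% of variance). A mean gap of Δ weeks shifts the standardised difference by d = r × Δ/1.44. With m = 47 × 3/π = 44.9 effective patients per arm:

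- chance of a false result in the favoured direction = Φ(d√(m/2) − 1.96)
- power if the gap masks a true 0.6 = Φ((0.6 − d)√(m/2) − 1.96)

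| r | Δ (weeks) | d | false result | power if masking |
|---|---|---|---|---|
| 0.3 | 0.5 | 0.10 | 7% | 65% |
| 0.3 | 1 | 0.21 | 17% | 46% |
| 0.3 | 1.5 | 0.31 | 32% | 28% |
| 0.5 | 0.5 | 0.17 | 13% | 53% |
| 0.5 | 1 | 0.35 | 38% | 22% |
| 0.5 | 1.5 | 0.52 | 69% | 6% |

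**4. Equal dwell, by simulation.** 47 per arm, latent effect 0.6 SD, four grades (45/35/16/4% in control), dwell uniform over 3-8 weeks. With no true effect, the crude test rejects in about 5% of trials, so the open date alone does not bias. With the effect present, crude power is about 67%. A van Elteren test over three planned-dwell strata has 73-76% if dwell explains 20-30% of variance, gains 1-2 points at 10%, and gains nothing at 0%. The crude figure is below 80% because of ties on a four-grade scale under the assumed distribution, which is a separate matter.

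**5. A gap in actual dwell, same model.** No true effect, control stents out about 1 week earlier:

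- Crude test: rejects in about 17-38% of trials across 10-30% of variance explained, against the supplement. Repeat runs put the lower end at 14-15%.
- Half-week gap: about 7-11%.
- Stratified on planned dwell: 30-46%, against 28-38% for the crude test in the same runs. It does not help and is slightly worse.
- Stratified on actual dwell: about 6-7%.

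With a true effect of 0.6 and the same 1-week gap, crude power is 32-36% at 10% explained, 20-23% at 20% and 13-16% at 30%. Stratifying on planned dwell still gives only 17-38% over that range.

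In the opposite direction (supplement stents out about 0.9 week earlier, no true effect), the crude test rejects in 13% (r = 0.3) to 27% (r = 0.5) of trials, nearly all in favour of the supplement.

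**The case against.** A reader might infer that removal dates are set after randomisation by clinics that watch pH and take placebo stents out sooner. The documents do not support this. Removal is described as programmed and following usual practice. Section 6.2.2 shows that a date can already exist at inclusion. No section makes pH a ground for removal. Paper diaries reach the clinic only at the removal visit; earlier sight through the online diary is possible but not stated. The opposite inference, that every patient must have a known date at V0, also goes too far: 6.2.2 only excludes those with an early date, and 6.2.1 admits patients whose stent is not yet placed.

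The trial is double-blind with the same stent-care instructions in both arms, so planned dwell is balanced in expectation. The size of any bias rests on assumed values. At 10% of variance explained and a half-week gap, null rejection is only about 8%. Stratifying on planned dwell does not repair a gap in actual dwell, and covariate adjustment is commonly left to an analysis plan, which is not shown here.

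All of this stands, and it limits the point to precision plus an unguarded route to bias. It does not remove the point: 8.2 states an unadjusted comparison, and no later analysis plan can recover a planned date that was never recorded before allocation.

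**Conclusion.** The point holds in a limited form. The primary score is read over a 2.7-fold range of time, dwell is collected, and the stated comparison does not use it. If dwell is balanced, validity is intact and the loss is one of precision: about 6-9 power points if dwell explains 20-30% of variance, 1-2 at 10%, none at 0%. Bias is conditional on an arm gap in actual dwell, which the documents neither describe nor exclude. A gap of about a week could create or hide a material part of the planned 0.6; a half-week gap does much less.

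These sizes rest on a uniform dwell distribution, an assumed share of variance, and time from V0 standing in for dwell. None of these comes from the protocol. The 6-7% for stratifying on actual dwell also treats dwell as an ordinary confounder; if treatment itself changes dwell, that adjustment is not clean.

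**What to change.** 1. **6.3.3:** record the planned extraction date, or planned dwell from placement, before the code is assigned, with a category for removal not yet scheduled.
2. **8.2:** stratify the primary Mann-Whitney test by planned dwell (van Elteren), for example in bands of 3 to under 5, 5 to under 6.5, and 6.5 to 8 weeks, plus the unscheduled category. This buys precision only.
3. **Reporting:** give actual dwell by arm, and actual minus planned dwell with the reason for each change.
4. **Sensitivity analysis:** repeat the comparison stratified on actual dwell counted from placement, labelled as adjusting for a post-randomisation variable.
5. **7.4:** reconcile the 8-week label for the final visit with the window in 6.3.4.

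The cost is one extra field and a stratified test in place of a simple one. Clinics keep control of the removal date.

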6.2.1 Inclusion criteria

- Age ≥18 years.
- Patients who have recently had a double J stent (time less than a week) or who have scheduled their placement and are recommended to control the pH to avoid scaling / calcification.
- Patients who agree to participate in the study and provide their informed consent.

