6.2.3 Discontinuation criteria

- Withdrawal of informed consent.
- Violation of the protocol.

- Patients with early withdrawal of the double J stent (time less than 3 weeks after the baseline visit).
- Use of other food supplements not specified in this protocol that could interfere with the evaluation of the efficacy of the supplement under study.
- Serious Adverse Event (AAG).
- Abandonment of the study.

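### The 3-week minimum counts only from the baseline visit although patients may enrol before stent placement, so a compliant stent dwell can be far below 3 weeks and power could be lost

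*Protocol*

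**What the plan says.** Section 6.2.1 opens two routes into the trial. In the first, the stent has been in place for less than a week. In the second, it is not yet in place: "or who have scheduled their placement and are recommended to control the pH to avoid scaling / calcification". Nothing limits how long after V0 the placement may fall.

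The time rules all refer to V0:

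- Section 6.2.2 excludes patients with extraction scheduled "before 3 weeks from the baseline / inclusion visit".
- Section 6.2.3 lists early removal as a discontinuation criterion, defined as "time less than 3 weeks after the baseline visit".
- Section 6.3.2 measures follow-up from V0 to the final visit (Vf), from 3 weeks to about 2 months.
- Section 6.3.4 leaves removal to usual practice, in a window "which should be between 3 and 8 weeks after the baseline visit".

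Under Section 6.3.3 the allocated product is handed over at the end of V0, whether or not a stent is in place. Section 7.1 names the 0–3 incrustation score as the main efficacy variable. Section 7.2 records placement date, removal date and total stent days, but as secondary variables. No eligibility rule uses stent days.

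**The concern.** A stent cannot encrust before it is in place. For a patient enrolled ahead of placement, the clock in the time rules starts before the period in which the main outcome can develop. The 3-week minimum then guarantees 3 weeks from V0 to removal, but not 3 weeks of stent dwell.

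If a stent is in place for only a few days, the score has little room to differ between arms. Each such patient counts towards the 94 evaluable patients in Section 6.8 while adding little to the contrast. The 10% allowance in that section is for losses, and a compliant patient with a short dwell is not a loss.

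**Working it through.** **1. Permitted dwell.** Let L be the days from V0 to placement. Removal is allowed from day 21 (3 weeks) to day 56 (8 weeks) after V0, so for a scheduled stent:

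minimum dwell = 21 − L

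| L (days) | Minimum compliant dwell (days) |
|---|---|
| 0 | 21 |
| 7 | 21 − 7 = 14 |
| 14 | 21 − 14 = 7 |
| 18 | 21 − 18 = 3 |
| 20 | 21 − 20 = 1 |

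For a stent already in place at V0 the minimum is 21 days or slightly more. The gap therefore concerns only patients enrolled before placement.

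**2. The protocol's sample size.** Section 6.8 gives the Mann-Whitney U test, effect size 0.6, 80% power, 94 patients, and 105 after a 10% loss. It states no significance level; two-sided 0.05 is assumed here. The normal approximation for two means gives 44 per arm. Dividing by the Mann-Whitney relative efficiency 3/π = 0.955 gives 44 / 0.955 = 46.1, rounded up to 47 per arm, or 94. Then 94 / 0.90 = 104.4, rounded up to 105. Both stated figures reproduce. A noncentral-t calculation with the same efficiency gives power 0.803 at 47 per arm.

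**3. Illustrative dilution, closed form.** Let f be the assumed share of patients with too short a dwell and r the assumed fraction of the effect they keep. Neither is in the protocol.

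diluted effect = 0.6 × [1 − f(1 − r)]

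| f | r | Diluted effect | Power, 47 per arm |
|---|---|---|---|
| 0 | – | 0.60 | 0.80 |
| 5% | 0 | 0.6 × 0.95 = 0.57 | 0.76 |
| 10% | 0.5 | 0.6 × 0.95 = 0.57 | 0.76 |
| 10% | 0 | 0.6 × 0.90 = 0.54 | 0.72 |
| 20% | 0.5 | 0.6 × 0.90 = 0.54 | 0.72 |
| 20% | 0 | 0.6 × 0.80 = 0.48 | 0.61 |

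**4. Illustrative dilution, simulation.** The 0–3 score was simulated with 47 per arm and several assumed control distributions. Short-dwell patients were set to 0 in both arms, and the test was Mann-Whitney. Power was about 73–79% at f = 5%, 66–77% at 10% and 51–69% at 20%. The spread reflects the assumed score distribution.

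**5. Combined range.** Taking steps 3 and 4 together gives about 73–79% at 5%, 66–77% at 10% and 51–72% at 20%.

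**The case against.** **The purpose of the 3-week rule is not stated.** Product is dispensed at V0, and pH self-monitoring runs from V0 to Vf. Counting from V0 therefore secures a minimum time on product, which is a coherent aim. This stands: a reader might infer that the rule was meant to secure dwell and that the anchor defeats it, but the protocol gives no reason for the rule. The sections do not contradict each other; the eligibility rule is incomplete.

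**Long lags may be rare.** Section 6.3.3 lists the placement date among the V0 data, and the cost objective in Section 3.2 runs from placement to withdrawal. Both suggest that V0 was expected near placement, but neither requires it. The share enrolled before placement and the lag are not given. A reader might infer that the outcome is in fact diluted; the protocol supports only that it could be.

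**The effect size may already allow for the mix.** Section 6.8 does not say whether 0.6 refers to patients with adequate dwell or to everyone enrolled. On the second reading, the stated 80% already includes some short dwell. This also stands, and is a further reason to treat the power figures as illustrative. Nor does the protocol give any figure for how stents score after a short dwell; Section 2 says only that encrustation is faster in some patients than in others.

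**Randomisation balances dwell, and dwell is recorded.** In expectation the arms are affected alike, so a reader who inferred bias towards the supplement or placebo would be wrong. Recorded stent days allow description or adjustment later, but adjustment cannot restore information from stents that had little time to encrust.

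**Long dwell is a separate matter.** A stent placed 6 days before V0 and removed on day 56 has 56 + 6 = 62 days in place. This shows that dwell varies, but it is not evidence of dilution, and the change proposed here does not affect it.

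**Conclusion.** The gap in the rules is certain; its effect on the trial is not. The protocol permits a dwell of 21 − L days with no limit on L, and nothing sets a minimum time from placement to removal. If such patients are enrolled in any number, the contrast on the main variable could shrink and power could fall below the planned 80%.

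The combined range in step 5 rests on four assumptions: the share with too short a dwell, how much effect those patients keep, the score distribution, and an effect of 0.6 that applies only to patients with adequate dwell. At a share of 5% or less the loss is modest. The case for acting is that the change is cheap, not that a large loss has been shown.

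**What to change.** In Section 6.2.2, count the protocol's own 3-week minimum to scheduled extraction from the later of V0 and stent placement. Planned dwell and planned product exposure are then both at least 3 weeks, and the 94 and 105 in Section 6.8 need no change on this account.

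Keep the upper limit of about 8 weeks or 2 months counted from V0. Moving it to placement would conflict with the 2 months of treatment in Section 1.17, the follow-up in Section 6.3.2 and the product supplied at baseline for the whole study in Section 10.1. With a 14-day lag, for instance, it would run to 14 + 56 = 70 days after V0. With the upper limit left at V0, the two rules together cap the lag at 56 − 21 = 35 days.

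Reconcile the wording of Sections 6.2.3, 6.3.2 and 6.3.4 with this. The actual time of removal stays with usual practice, as Section 6.3.4 already says.

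The cost is a wording amendment. A few patients enrolled before placement with early planned removal become ineligible, so recruitment would be slightly slower.
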